Supplemental appendices compiled in separate document, saved here: [x Protocol - appendix attachments\2017.11 Hyperlink 3 Protocol Appendices.pdf](#)

## 1. Background and Significance

### 1.A. Background

**1.A.1. Impact of the condition on the health of individuals and populations.** Abnormally high blood pressure (hypertension) is the most common chronic condition for which patients see primary care physicians, affecting 80 million (about one in three) U.S. adults, and is a major risk factor for heart attacks, stroke, heart failure, and kidney failure. The estimated direct and indirect cost of high blood pressure (BP) in 2011 in the U.S. was \$46.4 billion. Compared with other modifiable cardiovascular (CV) risk factors, poorly controlled hypertension is the leading cause of death among women and the second leading cause of death among men after smoking. About half of patients with hypertension in the U.S. do not have their BP controlled to recommended levels, and control rates are even lower in racial/ethnic minority and low socioeconomic status populations. Attaining BP control to recommended levels has been shown to lower the risk of future CV events (heart attacks and strokes), the most common global cause of death and disability.

**1.A.2. Previous research and gaps in evidence addressed by the proposed trial.** National data from 2003-2012 has shown some improvement in the control of hypertension to just over 50%, well below the goals set by Healthy People 2020 (61.2% by 2020), the Million Hearts Initiative (65% by 2017), and the American Medical Group Association Measure Up/Pressure Down campaign (80% by 2016). Although access to health care remains a barrier to attaining control, recent evidence suggests that 89% of people with uncontrolled hypertension have a regular source of health care, and 85% had insurance. Although high BP usually doesn't have symptoms, more than 80% of people with hypertension are aware they have it, and men, women, and Hispanic and black Americans all had awareness levels above 80%. Similarly, most patients with hypertension are being treated with medication (76%). There is currently little difference in treatment rates by race/ethnicity, although more women (81%) than men (71%) are treated. Patients with hypertension visit a physician, on average, 4 or more times a year, which should provide ample opportunity to detect and address uncontrolled hypertension. However, clinicians are often slow to start antihypertensive drugs or increase treatment intensity with higher doses and combinations of drugs, even when BP is elevated at several clinic visits, a complex phenomenon dubbed "clinical inertia." Patients also contribute by resisting advice to change their lifestyle, start medication, or take their medication as prescribed. Sometimes this resistance is related to stressful lives, side effects, medication costs, or not being convinced that their BP is a problem.

Thus, while improving access to care, awareness of hypertension and initiation of treatment for hypertension are important, addressing these factors in isolation is likely to result only in small improvements in hypertension control. Rather, the best current opportunities to improve BP control center on the way clinicians and patients interact in the health care setting. Research over the last several decades has shown that the most potent interventions are those that reorganize clinical practice to empower non-physician practitioners and patients to work together to encourage self-management, adjust antihypertensive therapy, and conduct follow up in a team-based approach to hypertension care. In a 2006 meta-analysis of 28 studies, most of which included a nurse or a pharmacist team member as a care manager, average BP dropped by 10/4 mm Hg, and the absolute proportion of patients achieving BP control improved by 20%. The largest BP effects were seen in studies in which the care manager was able to recommend treatment changes without further direct action by the physician. A recently updated meta-analysis including 31 additional studies confirmed these findings, albeit with somewhat smaller BP reductions (5/2 mm Hg, proportion achieving BP control improved by 12%). However, several of the studies included in the meta-analysis also suggested that team-based care for hypertension may simultaneously reduce cholesterol levels and improve blood sugar control in adults with diabetes, thus reducing long-term CV risk even further than would be achieved based on BP reductions alone. A modeling study

found that nationwide adoption of team-based care for uncontrolled hypertension could reduce uncontrolled hypertension by 13% and prevent 638,000 CV events over 10 years. Based on this strong evidence, the Community Preventive Services Task Force recommended team-based care to improve BP control. A key research gap identified in this systematic review was the need for more evidence on scalability of team-based care in large and diverse populations, multiple sites, and multiyear evaluations. In addition, few studies have measured patient-reported outcomes of team-based care, and the results of such measurements have been inconsistent.

Self-measured home BP monitoring has been identified as a useful, cost-saving adjunct to team-based care for hypertension in comprehensive evidence reviews. A recent systematic review concluded that home BP monitoring alone results in small BP reductions at 6 months compared with usual care (a difference of -3 mm Hg for systolic BP [SBP, the top number] and -2 mm Hg for diastolic BP [DBP, the bottom number]). In contrast, improved BP outcomes were greater in high-quality studies that combined home BP monitoring with additional support interventions for as long as 12 months (SBP reductions of -3.4 to -8.9 mm Hg, DBP reductions of -1.9 to -4.4 mm Hg). Additional support was defined as patient education, counseling, or telemedicine support. An individual patient data meta-analysis conducted by members of this research team reached similar conclusions. The biggest research gaps identified were the need to determine the long-term effects of home BP monitoring beyond 12 months and in key subgroups that are more likely to have difficulty with BP control (eg, older persons, those with more severe hypertension, those with CV disease, diabetes, or kidney disease).

Both patients and health care organizations are increasingly interested in alternatives to traditional clinic visits. Home BP monitoring is an essential ingredient for such alternatives for hypertension care. Our previous work on the Hyperlink study (R01 HL090965) used telemonitoring and telephone for communication between patients and pharmacists based in primary care clinics. Patients with uncontrolled hypertension in the intervention group safely achieved double the rate of sustained BP control compared with patients who continued to receive routine primary care. Previous research in other care settings has shown similar improvement in BP control without the need for clinic visits. However, some group practices have achieved very high rates of BP control using quality-improvement methods without routine use of home BP monitoring, telehealth, or expanded care teams. Thus, it is unclear whether these improve care for uncontrolled hypertension compared with clinic-based care that is organized according to current best practices.

National strategic planning groups for comparative effectiveness studies have identified the research gaps noted above as high priority topics. The Institute of Medicine has called for studies comparing the effectiveness of various strategies aimed at integrating pharmacists into primary care (eg, pharmacist-provided medication management to improve condition-specific outcomes). The Agency for Healthcare Research and Quality has cited self-measured BP as a topic needing future research, specifically calling for longer-term randomized controlled trials to examine clinical outcomes, identify subgroups likely to benefit, and clarify what types of additional support are most effective.

This pragmatic trial is aimed at improving hypertension care in a large health system and will address these research gaps by: **1)** Comparing two different organizational models for team-based care, one that incorporates current best practices but relies primarily on the physician-medical assistant dyad and face-to-face visits (clinic-based care) and one that extends team-based care outside the confines of the clinic by adding telehealth care coordinated by a pharmacist (telehealth care). **2)** Incorporating self-measured home BP telemonitoring as a systematic part of the telehealth care intervention in a long-term evaluation that is large enough to determine its effects in key subgroups. **3)** Measuring patient-centered outcomes as well as traditional clinical outcomes (eg, BP, other CV risk factors). **4)** Measuring and evaluating the implementation of a pragmatic, large-scale, long-term program of clinic-based care and telehealth care for patients with uncontrolled hypertension in the primary care setting using electronic data sources.

## 1.B. Significance

**1.B.1. Potential for the study to improve health care and outcomes.** This study will compare the clinical effectiveness and effects on patient-reported outcomes of two different models of team-based care for uncontrolled hypertension and study how the interventions are implemented in the real-world setting of a large health system. A large body of evidence from both observational and interventional studies has shown that even small reductions in BP result in substantial reductions in rates of heart disease and stroke. The estimated effect of lowering BP by 5 mm Hg diastolic reduces the relative risk of stroke by 34% and heart disease by 21% and stroke deaths by 40% and vascular disease deaths by 30%. Even SBP and DBP reductions as small as 2-3 mm Hg are predicted to reduce stroke by 10%-28% and heart disease by 5%-9%.

Numerous stakeholders have endorsed the need to improve hypertension care in the primary care setting, where most patients receive care. “Controlling high blood pressure” is a key national quality measure in the Healthcare Effectiveness Data and Information Set (HEDIS). This measure is publicly reported in Minnesota for all medical groups and published on the Minnesota Community Measurement Web site. Practice-based quality measures generally show higher levels of BP control than national levels because they include only diagnosed patients receiving care in the previous 2 years. These are useful for assessing important variations in practice. For example, in the state of Minnesota for 2015 dates of service, the average publicly reported rate of meeting recommended goals for hypertension control by all reporting medical groups is 77%, but individual medical groups range from 37% to 91%. HealthPartners clinics fell in the average range, at 75%, and also show substantial between-clinic variation. There is an 8% gap in BP control rates between white and black patients (unpublished data). The primary care, nursing, and pharmacy departments, each represented in this project as stakeholders, convened a working group to redesign primary care systems to improve hypertension control and make care more consistent. Our group faced uncertainty about the best methods to improve BP outcomes in clinical practice, a dilemma likely shared by many others.

### 1.B.2. Evidence for efficacy or effectiveness of the interventions being compared

**1.B.2.1. Best practice clinic-based care.** The clinic-based care approach we adapted for this project is based on elements from several programs that have been shown to be effective in other settings, albeit based mostly on observational evidence. Kaiser Permanente’s hypertension program was gradually implemented over more than a decade in Northern and Southern California and includes the following key elements: use of evidence-based guidelines, a comprehensive hypertension registry, regular measurement and feedback on performance metrics, medical assistant visits for BP measurement, and promotion of a simple treatment algorithm based on single-pill combination pharmacotherapy. This program was associated with improvement in hypertension control, according to the HEDIS measurement, from 44% in 2001 to 80% in 2009 in Northern California and from 54% in 2004 to 86% in 2012 in Southern California. Racial, ethnic, and language disparities in BP control were reduced. There was much less concomitant improvement in hypertension control in California at non-Kaiser practices (63.4% to 69.4%) and nationally (55.5% to 64.1%) during the same period.

Other groups have put forth similar recommendations for reorganizing clinic-based hypertension care: the American Medical Association’s STEPSforward program for clinical practice redesign, the American Medical Group Association’s Measure Up/Pressure Down campaign, and the Million Hearts program for controlling hypertension. Key elements include: 1) promotion of accurate BP measurement; 2) repeat measurement when BP is elevated; 3) addressing elevated BP at every visit; 4) use of an evidence-based standardized protocol, including low-cost medications and single-pill combination therapy, when possible; 5) reassessing the patient every 2 to 4 weeks until BP is controlled; and 6) partnering with patients and families to improve self-monitoring, adherence, and lifestyle changes. Registries are also considered an important component to track patients over time and between visits. Consistency with guidelines from 5 – Version 2018.07

other national organizations suggests that these constitute current best practices for clinic-based care. However, most of the individual elements of the recommendations are based on expert opinion, and even the well-publicized Kaiser model results are based on observational studies. Therefore, the evidence for best-practice clinic-based care would be strengthened greatly by comparing it to another care model using a rigorous research design.

**1.B.2.2. Telehealth Care.** We and others have found nurse- or pharmacist-led telehealth care with home BP monitoring to be a particularly effective intervention for lowering BP in patients with uncontrolled hypertension. A recent study among U.S. veterans compared a telemonitoring intervention with various types of nurse management to usual care. The largest effect was observed for combined behavioral and medication management in patients with uncontrolled BP (SBP was 15 mm Hg lower at 12 months and 8 mm Hg lower at 18 months than control). In 387 urban African-Americans with uncontrolled BP randomly assigned to community nurse-managed telemonitoring or usual care, intervention group patients had a 5 mm Hg greater reduction in SBP at 12 months. A trial conducted in UK primary care practices included automated text messages or email as part of a home BP telemonitoring intervention. BP was 4/2 mm Hg lower in the intervention patients than in the usual care patients after 6 months. In another recent study conducted in a managed care setting, patients randomly assigned to home BP telemonitoring combined with pharmacist-led care had greater reductions in SBP (-21 mm Hg) than usual care (-8 mm Hg) over a 6-month intervention period.

Two randomized trials conducted by members of this research team also strongly support combining telehealth care with home BP self-monitoring and management support by pharmacists. [name], et al conducted a cluster-randomized trial at HealthPartners comparing pharmacist-led care management plus home BP telemonitoring with usual primary care in 450 patients with uncontrolled hypertension. Unlike many previous studies, there were few exclusion criteria, and patients with a broad range of comorbidities and hypertension severity were enrolled. The intervention patients had an 11/6 mm Hg greater drop in BP than the usual care patients at 6 months ( $P<0.001$ ), and a much higher proportion had controlled BP (72% vs. 45%,  $P<0.001$ ). The improved BP results were sustained with less intensive pharmacist contact at 12 months and 18 months (6 months after the intervention ended). A trial by [name], et al in a managed care setting used secure email messaging to send home BP data to pharmacists for 12 months. The intervention group had lower BP (14/7 mm Hg vs. 5/4 mm Hg,  $P<0.001$ ) and better BP control (56% vs. 31%,  $P<0.001$ ) than usual care.

The effect of telehealth care on patient-centered outcomes is much less well-studied than BP outcomes. A qualitative analysis of the UK trial of telemonitoring with automated patient decision support found that intervention patients and clinicians felt more confident in treatment decisions based on home BP. Before the intervention, they were hesitant to increase medication based on BP measurements taken on a single day in the clinic. Conversely, they perceived that multiple telemonitoring measurements were more accurate, were difficult to ignore, and led to action. In the previous study at HealthPartners, the intervention was associated with significant improvements in patient satisfaction with aspects of their care (clinicians listening carefully, explaining things clearly, and respecting what the patients said). Patients also reported feeling more able to communicate with their health care team, to incorporate home BP monitoring into their routine, and to keep their BP under control. In the study by [name], patients who worked with pharmacists reported strong and consistent improvements in the way their care reflected principles outlined for high-quality chronic illness care.

Members of the investigator team for this proposal have conducted a meta-analysis and computer-model simulation to predict outcomes of team-based care for hypertension in large populations. This suggests sizable potential for benefit of interventions for uncontrolled hypertension that include a pharmacist or nurse who can adjust medications, provide education and counseling on adherence and lifestyle, and support self-management. Based on data from 30 studies, these interventions led to, on average, a reduction of SBP of about 8 mm Hg, reductions in LDL-cholesterol ("bad" cholesterol) by about 12 mg/dL, and increases in HDL-cholesterol ("good" cholesterol) by about 1 mg/dL. The analysis

showed that, over 10 years, widespread adoption of this type of team-based care would reduce the number of persons with uncontrolled hypertension by 4.7 million (about 13%) and avert 192,000 heart attacks and 204,000 strokes.

**1.B.2.3. Need for a study comparing clinic-based and telehealth care models.** In summary, we have identified gaps that support the need for a comparative effectiveness trial. **1)** Although clinic-based care has achieved high levels of BP control in some highly integrated, large health systems, few practices have achieved the same outcomes. Rigorous evidence supporting most of the best practices is lacking. **2)** Despite strong evidence from research studies showing that nurse- and pharmacist-led team-based care and telehealth interventions result in large and lasting improvements in BP, it is unclear how successfully these can be implemented at scale in real-world settings without research support. **3)** It is also uncertain whether such resource-intensive care achieves better clinical results, and **4)** it is not known how it affects patient experience compared with traditional clinic-based care if best practices were adopted. The research will directly compare long-term outcomes of two different organizational models for team-based care, one that incorporates current best practices but relies primarily on the physician-medical assistant dyad and face-to-face visits (clinic-based care), and one that extends care outside the confines of the clinic using telehealth care, systematic home BP telemonitoring, and care coordination by a pharmacist or nurse practitioner (telehealth care). HealthPartners, the setting for the study, already uses some of the components of best practice in its clinic-based care, but further improvement in BP results is needed. HealthPartners is therefore poised to adopt other elements of best practice for clinic-based care (eg, protocols to promote consistent treatment and follow up for elevated BP, a hypertension registry to improve population management), but there are no plans to adopt telehealth care for hypertension widely in clinical practice without the research infrastructure to compare it rigorously with clinic-based care provided by this proposal. The study will support systematic data collection and analysis on implementation and outcomes, but intervention clinical care costs are supported by HealthPartners.

## **2. Objectives**

### **2.A. Aim 1**

In a pragmatic cluster-randomized trial in patients with uncontrolled hypertension, compare the effects of two evidence-based strategies on lowering blood pressure and other outcomes important to patients: best-practice clinic-based care and home-based telehealth care.

**Hypothesis 1.1:** Compared with patients in clinics assigned to clinic-based care, patients in clinics assigned to telehealth care will have a 5 mm Hg greater change in systolic blood pressure over 12 months of follow up.

**Hypothesis 1.2:** Compared with patients in clinics assigned to clinic-based care, patients in clinics assigned to telehealth care will report: a) fewer treatment side effects; b) better ratings of patient experience of hypertension care; and c) higher self-monitoring rates and confidence in self-care.

### **2.B. Aim 2**

Conduct an evaluation of reach, adoption, implementation, and maintenance of the telehealth care and clinic-based care interventions using a mixed-methods approach supported by the RE-AIM framework and the Consolidated Framework for Implementation Research (CFIR)

## **3. Study Design**

The study compares two alternative health care service designs emerging as the dominant choices for clinicians and health systems wanting to redesign and improve hypertension care outcomes. It builds on previous hypertension quality improvement initiatives and the Hyperlink study, which used telemonitoring and telephone communication between patients and clinical pharmacists. The study design incorporates many elements of pragmatic trials: few exclusion

criteria, flexible interventions delivered in routine care, and routine follow up to determine outcomes. It is a cluster-randomized comparative effectiveness trial in 20 primary care clinics (Figure 1). [Note that 21 primary care clinics were eligible to participate (see section 4.B.) and agreed to be randomized. Four of the clinics were co-located in two buildings (two practices in each) and had shared nursing leadership. Each of the co-located clinics were randomized as one unit; therefore there are 19 units of randomization. For simplicity throughout the rest of this protocol we will continue to refer to the study as including 20 primary care clinics.] The clinic-based care approach will use recommended best practices in ~10 clinics and ~1000 patients. It relies primarily on the physician-medical assistant dyad and face-to-face visits. The telehealth care approach adapts and implements a successful research-tested model in ~10 clinics and ~1000 patients. It differs from clinic-based care through the systematic use of home BP telemonitoring and home-based telehealth care coordinated by a pharmacist. Aim 1 compares outcomes that are important to patients and other stakeholders, including BP lowering, treatment side effects, patient experience, and self-care. Aim 2 evaluates the extent and between-clinic variability of the adoption, implementation, maintenance, and reach of the interventions. Data collected for Aim 2 will also be used to monitor and improve fidelity to the interventions. Please see Appendix F for a high level overview of the study design.

To ensure that the study addresses the relevant questions and concerns of patients, caregivers, clinicians, and other healthcare stakeholders, the research team includes two patient investigators, a patient advisory board (PAB), and a stakeholder advisory board. The roles, structure and function of these individuals and groups are described more fully in section 13 (Organization) and Appendix I.

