#### **4.D. Enrollment of patients**

For patients who have an elevated BP at a primary care encounter (nurse or provider) but do not yet meet the study's high BP criteria for two consecutive qualifying visits, providers and clinic staff are encouraged to use a standardized hypertension referral order that facilitates scheduling a BP follow up with a provider of their choice (nurse, primary care provider, MTM pharmacist, or specialist).

If the patient meets all study inclusion and exclusion criteria, the patient will be identified automatically upon BP entry through algorithms within a web-service and flagged as "eligible" for Hyperlink. The MA will receive a best practice alert (BPA) that if accepted will open an order for hypertension follow up. The MA will "pend" this order for the provider. Once pended, the order can be removed or signed, but must be addressed by the provider before the encounter can be closed. The follow-up BP order contains defaults to nurse, PCP, or MTM as dictated by appropriate clinic-based care or telehealth care depending on the clinic assignment (see section 5 on Interventions.) The defaults can be modified by the provider prior to signing order using their professional judgement. Once the order is signed and the encounter is closed, the patient is flagged as "enrolled" in the study.

Enrollment will occur in two phases, Vanguard and Main Trial. Vanguard Phase enrollment will begin at the start of Year 2 with 2-4 Vanguard clinics to test procedures and make adjustments so that they are running smoothly. Enrollment of patients will continue until the study sample of 2000 eligible patients has been enrolled in the main trial from the 20 study clinics (Figure 1). In order to avoid very unequal distribution of cluster sizes, enrollment will continue for each clinic until a cap is met (e.g., 200 in a large clinic) or until a minimum is met (e.g., 40 in a small clinic). An average-sized clinic would need to enroll about 8-10 patients per month (or 2-3 patients per week) over 12 months to achieve our sample size.

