### 10.A.1. Aim 1 Other Analyses

We plan to explore whether treatment effects differ among patient groups defined by age, race/ethnicity, socioeconomic status, and comorbidity. While we anticipate that on average across all patient groups telehealth care will reduce SBP by 5 mm Hg more than clinic-based care, we will separately quantify the treatment effect for all H1 outcomes among targeted patient subgroups. The H1 analytic models can be easily adapted to include parameters for patient covariates as well as interactions of patient covariates with time or time by treatment.

[figure not shown]
The H1 analytic models can be readily adapted for secondary and sensitivity analyses. As presented, H1.1 assumes a linear rate of change in SBP over time. The model can be readily adapted to assess the immediate effectiveness of telehealth during the first 6 months following eligibility separately from the 6- to 12- and 12- to 24-month periods, when short-term improvements in SBP or PROs may be differentially maintained over a longer time frame. Similarly, parameters  $\gamma_{01}$  and  $\gamma_{11}$  can be allowed to vary randomly so that the rate of SBP change is different for each of the 20 randomized clinics. We could then assess, for example, whether clinic-specific rates of change are related to clinic characteristics or the fidelity with which the care model was implemented.

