### 10.A.3. Power for Aim 1 Analyses

A power analysis estimated the minimum detectable standardized effect (MDSE) for  $\gamma_{11}$  in the H1.1 model under a range of assumptions about the number of SBP values from each eligible patient and the intraclass correlation (ICC) in SBP values due to patients’ receiving care at the same clinics. We used data from patients (age 18-85, diagnosed with hypertension, current visit BP  $\geq 150/95$ , most recent previous encounter BP  $\geq 150/95$ ,  $\geq 1$  follow-up visit) seen 5/1/2017 through 2/28/2018 in the randomized Hyperlink clinics to inform power analysis assumptions. These patients (N=4967) had M=3.3 SBP over 10 months (Median=3, range 1-23), index  $M_{SBP}=159.9$ , index  $SD_{SBP}=16.1$ , all BP  $M_{SBP}=150.7$ , all BP  $SD_{SBP}=20.4$ , and a 3-level variance components model of SBP estimated  $ICC_{clin}=.003$  and  $ICC_{pt}=.28$ . For power estimates, conservatively assumed n=100 eligible patients in each of 20 clinics, 3 SBP per patient over 24 months and  $ICC_{clin}=.01-.03$  in a 2-level variance components model.

Under these assumptions, the H1.1 analysis is powered (80%,  $\alpha_2=.05$ ) to detect  $\gamma_{11} < -.124$  (when  $ICC_{clin} = .01$ ) and  $\gamma_{11} < -.174$  (when  $ICC_{clin}=.03$ ) so that an annual reduction in SBP that is  $20.4 * (.124-.174)=2.53-3.55$  mm Hg greater among patients in telehealth relative to clinic-based care clinics will be statistically detectable. Based on our previous research and systematic reviews, we believe a 5 mm Hg greater reduction in SBP will be achieved in eligible patients in telehealth care compared with clinic-based care. We assert that 5 mm Hg is a clinically important reduction in BP that substantially lowers the risk of stroke and heart disease, and even smaller reductions of 2 or 3 mm Hg have clinically important effects. The analysis should be sufficiently powered to observe clinically meaningful between-group differences in SBP reduction.

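### The stated detectable effects assume 20 equal clinics, but 19 units of unequal size were randomised; at the plan's own ICCs they are somewhat too favourable, and the cluster level and degrees of freedom are not defined

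*Combined protocol and SAP*

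**What the plan says.** - **Units.** Section 3 (Study Design) reports 21 eligible practices, four of them sharing two buildings, with each co-located pair randomised together: "therefore there are 19 units of randomization". It adds: "For simplicity throughout the rest of this protocol we will continue to refer to the study as including 20 primary care clinics".
- **Power.** Section 10.A.3: "conservatively assumed n=100 eligible patients in each of 20 clinics, 3 SBP per patient over 24 months", with a clinic ICC of .01 to .03. The result for 80% power at two-sided .05 is a standardised effect of .124 to .174, or 2.53 to 3.55 mm Hg using an SD of 20.4. The planning data in the same section gave a clinic ICC of .003 and 3.3 readings per patient over 10 months.
- **Cluster sizes.** Section 4.D enrols at each clinic "until a cap is met (e.g., 200 in a large clinic) or until a minimum is met (e.g., 40 in a small clinic"). Section 15, item 2.2, plans no enrolment target per clinic and looks for roughly 50 patients from the smaller ones.
- **Model.** Section 10.A gives H1.1 a random intercept for randomised clinics and states no number of levels. An optional extension in section 10.A.1 lets slopes vary so that "the rate of SBP change is different for each of the 20 randomized clinics". Section 10.A.4 says the maximum-likelihood models cope with unequal numbers of patients per clinic. No method for degrees of freedom is given.

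**The concern.** In a cluster trial, the information about treatment is limited by the number of units that were assigned independently. Here that number is 19, and none of the counts in the section 3 note is 20. The shorthand is harmless in prose, but in section 10.A.3 it is an input to a calculation, combined with equal cluster sizes that the enrolment rules do not deliver. Fewer units, unequal sizes and a reference distribution suited to about 17 cluster-level degrees of freedom each raise the detectable effect.

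The same gap leaves the analysis open. If the random effect were indexed by practice, two practices in one building that were assigned together and share nursing leadership would enter as separate clusters. At stake are the accuracy of a published power figure and a choice about the primary analysis that should be fixed before the data are seen.

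**Working it through.** **Inputs.** N = 2000, 20 clinics of 100, 3 readings over 24 months, ICC ρ = .01 and .03, SD 20.4, power 80%, two-sided .05 (section 10.A.3); 19 units (section 3), hence 9 v 10; example limits of 40 and 200 (section 4.D). Assumed, because the documents do not give them: readings at years 0, 1 and 2, and the size CV.

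**1. The plan's figure.** With z.975 + z.80 = 2.8016 and a time sum of squares of 2 per patient:

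MDSE = 2.8016 × √[2(1−ρ)(1+99ρ)/(1000×2)]

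- ρ = .01: 2.8016 × √(.99 × 1.99/1000) = .1244, or 2.54 mm Hg.
- ρ = .03: 2.8016 × √(.97 × 3.97/1000) = .1739, or 3.55 mm Hg.

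These match .124 and .174. The plan shows no formula, so the match, including the normal reference, is inferred.

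**2. Nineteen equal units.** m = 2000/19 = 105.26, so the arms have 947.4 and 1052.6 patients.

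SE² = (1−ρ)[1+(m−1)ρ]/2 × (1/947.4 + 1/1052.6)

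- ρ = .01: SE = .0450; 2.8016 × .0450 = .126, or 2.57 mm Hg (+1.5%).
- ρ = .03: SE = .0634; 2.8016 × .0634 = .178, or 3.62 mm Hg (+2.1%).

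**3. t reference, 17 df.** The multiplier rises from 2.802 to 2.973 (×1.061), giving 2.73 and 3.84 mm Hg (+7.7% and +8.4%).

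**4. Unequal sizes.** A uniform spread over 40–200 has SD 160/√12 = 46.2. Divided by its mean of 120 that is a CV of .38; divided by 105.26 it is .44. I take .4 to .5.

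- *Mixed-model weighting.* A unit of size n contributes n/(1+(n−1)ρ), and SE² = [(1−ρ)/2](1/9+1/10) ÷ (mean contribution). With gamma-distributed sizes the mean contribution at ρ = .01 and .03 is 49.5 and 24.7 (CV .4), or 48.5 and 24.3 (CV .5). Equal sizes give 51.5 and 25.5.
- *Size-weighted design effect.* 1 + [(1+CV²)m − 1]ρ. This is cruder and does not match how the planned model weights clusters.

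| 19 units, t(17) | ρ = .01 | ρ = .03 |
|---|---|---|
| CV .4, mixed-model weighting | 2.79 | 3.90 |
| CV .5, mixed-model weighting | 2.82 | 3.94 |
| CV .4, size-weighted | 2.84 | 4.07 |
| CV .5, size-weighted | 2.90 | 4.19 |

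Uniform or two-point sizes change the mixed-model rows by about 0.03 at most.

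**5. Bounds.** With every unit at either 40 or 200 (CV about .75), the size-weighted formula, t(17) and ρ = .03, the detectable effect is about 4.6 mm Hg and power for 5 mm Hg is about 86%. At CV .4 by the same formula, power is 93%. At the planning ICC of .003, 19 units with CV .4 and t(17) give 2.24 mm Hg.

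**6. The model as written.** With only a clinic random intercept and common reading times, the intercept cancels from the treatment-by-time contrast. Its SE, in residual SDs, is √[½(1/n₁+1/n₂)]. For 19, 20 and 21 equal units this is .0317, .0316 and .0317. The count matters only through the split between arms. The design effect in step 1 therefore describes between-cluster variation in slopes that the basic model does not carry.

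**7. H1.2.** 2.8016 × √[2(1+59ρ)/600] gives .239 and .269 at ρ = .02 and .03, against the stated .239 to .270. That base is 60 responders per clinic. Keeping 1200 responders in 19 equal units (m = 63.16), SE² = [1+(m−1)ρ](1/568.4 + 1/631.6). With t(17) this gives .257 and .291. The size-weighted formula at CV .5 gives .275 and .314.

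**The case against.** The strongest reply is that little of this is hidden or consequential. Section 3 discloses the 19 units and declares 20 to be shorthand. Moving from 20 to 19 alone adds only about 2%. The rest comes from a t reference and a CV that the documents do not state, and the limits of 40 and 200 are examples in a sentence whose purpose is to prevent very unequal clusters. The power calculation also carries real margin: an ICC 3 to 10 times the planning estimate, and 3 readings over 24 months when 3.3 were seen in 10. All of that stands, and it means the word 'conservatively' is fair for the ICC and for the readings. It is not fair for the number or the equality of clusters.

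Three stronger readings might be inferred, and the documents do not support them.

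- *That H1.1 itself assumes 20 equal clinics.* Section 10.A states no count, section 10.A.4 allows unequal clinics, and the mention of 20 in section 10.A.1 is shorthand in an optional extension. The fault is an unspecified level, not a wrong one.
- *That the confidence intervals are too narrow because 20 replaces 19.* Step 6 shows that the SE in the intercept-only model hardly depends on the count.
- *That the detectable effect rises to 4.2 mm Hg.* That needs the size-weighted formula. Under the planned type of model the total rise is about 10 to 11%.

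**Conclusion.** The concern holds for the power statement and for the missing definition of the cluster. At the plan's ICCs, 2.53 to 3.55 mm Hg should read about 2.57 to 3.62 for 19 equal units, 2.7 to 3.8 with t on 17 df, and about 2.8 to 3.9 with a size CV of .4 to .5. These figures rest on inferred reading times, a 9 v 10 split and an assumed CV. None reaches 5 mm Hg, so the sample size and the conclusion of section 10.A.3 stand, and a reader should not infer that H1.1 is underpowered. For H1.2 the margin is thinner: at ICC .03 the restated figure lies close to the upper end of the .20 to .30 range that section 10.A.3 uses as its benchmark, and slightly above it under the cruder formula.

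**What to change.** 1. In section 10.A, index the cluster random effect in H1.1 and H1.2 by the 19 randomised units, with each co-located pair as one level.
2. Name a small-sample method for the treatment contrast, such as Kenward-Roger; the cluster-level df are about 17, and fewer if strata are fitted. For H1.1, say whether the treatment-by-time contrast carries between-cluster variation through a cluster random slope, because the df correction has effect only if it does.
3. In section 10.A.3, restate the H1.1 and H1.2 detectable effects for 19 units with a stated size CV, the reference distribution, the formula and, for H1.2, the number of responders used.
4. Limit 'conservatively' to the ICC and the readings per patient.

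The cost is plan wording, one recalculation and slightly less favourable stated figures. No extra patients and no change to the design are needed.
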